**Title: Bubble PEP Training Among Patient
With Chronic Obstructive Pulmonary
Disease in Pulmonary Function Effects**

Study Protocol

Principal Investigator : [name]
ClinicalTrials.gov number: NCT04828837

2021/02/25

Material and Methods

Design and Participants

A randomized controlled trial with a single-blind study design was conducted. Using convenience sampling, data were collected from February 2021 to July 2021 at two teaching hospitals in northern Taiwan. Random serial numbers were generated by a research assistant using Random Allocation Software. The research assistant then put each serial number into an opaque envelope. After agreeing to participate in this study, each participant received an envelope and opened it to find out whether they belonged to the experimental group or the control group. The research assistant who assisted with recruitment did not engage in data collection or analysis.

The inclusion criteria were patients who diagnosed AECOPD and were 40 years old or older, conscious, could read articles, agreed to participate in the study, and signed an informed consent document. Exclusion criteria included patients who had used non-invasive PEP treatment before or during hospitalization, who had a mental disorder. The G*Power 3.1.9.7. software was used to estimate the sample size. A sample size of at least 26 has 80% power to detect the largest effect size of 0.5. An alpha level of 0.05 was used.

Measurements

The participants' demographics and clinical characteristics were collected, including gender, age, marital status, occupation, smoking history, chronic comorbidities (hypertension, diabetes mellitus, heart disease, lung cancer, and pneumothorax), COPD stage and dry powder bronchodilator use.

Chinese Version of the CAT

A total of eight items were used to assess the degree of dyspnea of the patients. Each item had a score ranging from 0 to 5 points, with the highest total score being 40

points. The higher the score, the higher the degree of dyspnea (Pothirat et al., 2015). The present study Cronbach's α was 0.88, and the Intraclass Correlation Coefficient (ICC) was 0.8.

CSSAQ

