After the experimental and control groups agreed to participate in this study and completed the consent forms, the two groups took pre-tests, which measured the Chinese version of the CAT, the CSSAQ, and the PEFR, within 48 hours of hospitalization, which served as the baseline of the intervention (T0). Data were collected again on the 7th day (T1) and the 30th day (T2) of the intervention to evaluate the effect of the intervention on pulmonary function. Only the experimental group received bubble PEP training, while the control group had routine medical care. If participants were discharged from the hospital in the middle of the study, the investigator monitored the intervention effectiveness via weekly follow-up telephone calls.

The study procedures are shown in Figure 1. Of the 57 patients who met the criteria were invited to participate for study eligibility. 14 of the remaining 27 participants, 13 and 14 were assigned to the intervention and control groups, respectively. 7days follow-up (T1) data were obtained for 17 of the participants. 1M follow-up (T2) analyses were performed among the 14 participants with complete data. The attrition rates were 30% and 71% for the experimental and control groups, respectively, with an overall attrition rate of 52%.

Ethical considerations

The study protocol was reviewed and approved by the Institutional Review Boards of Fu Jen Catholic University Hospital and En Chu Kong Hospital (FJUH109078 & ECKIRB1091006). Participants were required to sign informed consent forms before

the study and were allowed to terminate or withdraw from the study at any time. Data collected from the participants were coded, de-identified, and kept in a locked cabinet (ClinicalTrials.gov number: NCT04828837).

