**Title: Bubble PEP Training Among Patient
With Chronic Obstructive Pulmonary
Disease in Pulmonary Function Effects**

Statistical Analysis

Principal Investigator : [name]
ClinicalTrials.gov number: NCT04828837

2021/02/25

Statistical Analysis

Statistical analyses were performed using the IBM statistical software SPSS Statistics version 22. The intention-to-treat analysis (ITT) method was employed for data analysis, and the expectation-maximization algorithm (EM) was used to handle missing data. We used t-tests for independent samples, and Fisher's exact tests when more than 20% of cells have expected frequencies <5 or less than 10 observations to examine the homogeneity between groups based on demographic characteristics. Descriptive statistics, including count, percentage, mean, and standard deviation, were used to summarize the data. The intervention effect was evaluated using the generalized estimating equation (GEE) statistical method. Two-tailed tests were conducted, and p-values less than .05 were considered statistically significant.

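### The GEE test carries no small-sample correction for 27 patients: if a robust variance is used, the nominal .05 test rejects at about 7–9% with complete data and about 8–15.5% on available data

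*SAP*

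**What the plan says.** The SAP's Statistical Analysis section gives one sentence on the treatment comparison: "The intervention effect was evaluated using the generalized estimating equation (GEE) statistical method". The threshold follows: "Two-tailed tests were conducted, and p-values less than .05 were considered statistically significant". The only technical detail is the software: "Statistical analyses were performed using the IBM statistical software SPSS Statistics version 22". The section also calls for intention-to-treat analysis, with the EM algorithm for missing data. It does not state the working correlation, whether the variance is robust or model-based, which term is tested, the reference distribution, or any adjustment for few patients.

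The Protocol's Design and Participants section gives the planned size: "A sample size of at least 26 has 80% power to detect the largest effect size of 0.5". Its Procedures section gives the allocation: "14 of the remaining 27 participants, 13 and 14 were assigned to the intervention and control groups, respectively". There are three visits: a baseline, and then "Data were collected again on the 7th day (T1) and the 30th day (T2) of the intervention". Day-7 data exist for 17 patients. For day 30 it says: "1M follow-up (T2) analyses were performed among the 14 participants with complete data". The same section gives attrition of 30% and 71% by arm and 52% overall.

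**The concern.** In a GEE with a robust (sandwich) variance, the Wald test is justified by a large number of independent clusters. Here the clusters are patients, about 13 per arm at best and possibly 4 controls at day 30. With so few, the uncorrected sandwich variance is biased downward, and a normal or chi-square reference ignores the uncertainty in that variance. Both push towards rejecting too often.

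GEE is the only test of effect that the SAP names, so conclusions on CAT, CSSAQ and PEFR all rest on it. A borderline significant result could come from the method. Any confidence interval taken from the same fit would be too narrow. The small cluster count was foreseeable from the planned minimum of 26, before any dropout.

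**Working it through.** **Inputs from the documents.** Two-sided .05 and GEE (SAP); planned minimum 26, and 27 randomised as 13 vs 14, three visits, 17 with day-7 data (Protocol). Day-30 numbers from the attrition rates:
- 0.30 × 13 = 3.9, so 4 lost and 9 left.
- 0.71 × 14 = 9.94, so 10 lost and 4 left.
- Total 13; and 0.52 × 27 = 14.04 lost, which also leaves 13.

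The Protocol states 14. Both 9 vs 4 and 9 vs 5 were therefore used.

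**The plan's own figure.** A two-sample comparison at d = 0.5 needs 2 × (1.96 + 0.842)² / 0.25 = 62.8, so 63 per arm or 126 in total, not 26. The 26 is recovered from a repeated-measures ANOVA between-groups test with f = 0.5, correlation 0.5 and two measurements: noncentrality = f²Nm / [1 + (m − 1)ρ] = 0.25 × 26 × 2 / 1.5 = 8.67, power 0.806 (N = 24 gives 0.771). The Protocol states none of these inputs. The point here needs only the size, 26–27.

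**Direct check, all 27 complete.** In a saturated group-by-time model, the day-30 coefficient is the difference between arms in mean change from baseline. The robust variance divides by n where the unbiased one divides by n − 1:
- Variance ratio = [(12/13)/13 + (13/14)/14] / [1/13 + 1/14] = 0.1373 / 0.1484 = 0.926.
- SE ratio = √0.926 = 0.962.
- Effective critical value on the t scale with 25 df = 1.96 × 0.962 = 1.886.
- Two-sided error = 2 × P(t₂₅ > 1.886) = 7.1%.

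The normal reference alone gives 2 × P(t₂₅ > 1.96) = 6.1%. The downward-biased variance adds the rest.

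**Simulation under no effect.** Normal outcomes, equal variances, exchangeable true correlation, saturated group × time, dropout unrelated to outcome. Set A: correlation 0.5–0.7, day-7 split assumed 10/7, 9 vs 4 at day 30, 5,000 runs (2,000 for EM). Set B: correlation 0.3 or 0.6, day-7 split assumed 11/6, 9 vs 4 or 9 vs 5 at day 30, exchangeable or independence working correlation, 6,400 runs (3,200 for EM).

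Uncorrected robust variance, z or chi-square reference:

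| Data analysed | Day-30 contrast | Joint 2-df test |
|---|---|---|
| 27 complete | A 6.8%; B 6.9–7.3% | A 8.8%; B 8.8–9.3% |
| Available data | A 11.4–11.6%; B 8.0–11.5% | A 15.2–15.3%; B 11.2–15.5% |
| Completers only (B) | 11.2–13.4% | 16.1–21.5% |
| Single EM fill, group not in EM model (B) | 5.7–6.4% | 6.9–7.2% |
| Single EM fill, group in EM model (B) | 30–34% | 46–50% |

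Model-based variance instead (B), day-30 contrast / joint test:
- 27 complete: 5.6–5.8% / 5.7–6.1%.
- Available data, exchangeable working correlation: 6.3–9.1% / 7.3–11.1%.
- Available data, independence working correlation: 1.5–3.8% / 0.8–2.9%.

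Mancl-DeRouen variance with a t reference on n − 2 df, day-30 contrast:
- Set A: 3.9–4.5%.
- Set B: 4.1–4.3% with 27 complete, 3.5–5.3% on available data, 4.4–4.8% in completers.
- After a single EM fill with group in the EM model: still 25–28%.

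Monte Carlo standard error, √[p(1 − p)/runs], is about 0.3 points at 7% and 0.4 at 11.5% with 6,400 runs, and 0.8 at 30% with 3,200.

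**The case against.** The strongest reply is that the SAP never says the variance is robust. With a model-based variance and 27 complete patients, the error is about 6%, hardly worth arguing over. This stands as a limit on the size: a reader might infer that the plan has a false-positive rate of 6–15% outright, and the documents do not support that. It does not rescue the plan, because on available data the model-based rate runs from about 1% to 11% according to a working correlation that is also unstated.

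Second, the figures above 10% come from a GEE on observed data, whereas the SAP plans to fill gaps by EM, and the joint 2-df test is not named in the SAP. Both are true. The error under an EM fill could be about 6–7% or 30–50%, depending on whether group is in the EM model, which the SAP does not say. The Protocol's report of day-30 analyses among patients with complete data leaves open which data set was used.

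Third, a reader might infer that correcting the sandwich variance is enough whatever is done about EM. It is not: 25–28% remains when the fill includes group. The excess with all 27 complete shows, however, that the small-sample problem exists without any missing data.

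Nor was the trial planned at 27: the plan was at least 26, and 27 is the number randomised. The SAP does not mention confidence intervals, so their narrowness is a consequence for any that are reported, not an error in stated output.

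**Conclusion.** The point holds in conditional form. The SAP tests the intervention effect by GEE at two-tailed .05 with no small-sample correction, at a size where the correction matters. If the robust variance is used with a z or chi-square reference, the actual error is about 7% (day-30 contrast) and 9% (joint test) with all 27 complete, and about 8–12% and 11–15.5% on available data. With a model-based variance the excess is small at 27 complete, and on available data its direction and size depend on the working correlation.

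The calculation at 27 complete rests on normal outcomes and equal variances. The available-data ranges rest also on correlations of 0.3–0.7, an assumed day-7 split of 10/7 or 11/6, and dropout unrelated to outcome. Attrition of 30% against 71% makes that last assumption doubtful; the possible bias from dropout is a separate matter that these figures do not measure. The change is worth making, but it does not by itself invalidate the trial.

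**What to change.** Replace the uncorrected GEE Wald test. The preferred choice is a restricted-maximum-likelihood mixed model for repeated measures on the observed data, with Satterthwaite or Kenward-Roger degrees of freedom, naming the tested contrast and reporting its confidence interval. This also avoids treating EM-filled values as if they had been measured. Its error rate was not simulated here.

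If GEE is kept, state the working correlation and contrast, use a Mancl-DeRouen or Kauermann-Carroll variance with a t/F reference, and fit it to the observed data, not to a single EM fill. The simulations cover Mancl-DeRouen only. Neither option removes bias if dropout depends on unobserved outcomes.

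The cost is a short SAP amendment and a re-run. The documents do not show whether SPSS 22 offers each method, so this needs checking and other software may be required. The statistical cost is wider intervals and larger p-values, so a borderline result may lose significance.

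### The SAP gives the T0 values of CAT, CSSAQ and PEFR no role in the GEE and names no effect contrast; a T0-adjusted contrast should be specified

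*SAP*

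**What the plan says.** On the effect analysis, the SAP says only: "The intervention effect was evaluated using the generalized estimating equation (GEE) statistical method". It does not say whether T0 is a response, a covariate or left out, whether there is a group-by-time term, or which coefficient is the intervention effect.

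The Protocol (Procedures) shows that the baseline values are planned for everyone: "the two groups took pre-tests, which measured the Chinese version of the CAT, the CSSAQ, and the PEFR, within 48 hours of hospitalization". On follow-up it says: "Data were collected again on the 7th day (T1) and the 30th day (T2) of the intervention". On numbers: "13 and 14 were assigned to the intervention and control groups, respectively".

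The only baseline step in the SAP is a set of tests "to examine the homogeneity between groups based on demographic characteristics". T0 outcome scores are not mentioned there, and nothing says that the test results feed into the GEE.

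**The concern.** The T0 value of an outcome is usually the best available predictor of its later value. Here it is collected on all three outcomes, "within 48 hours of hospitalization, which served as the baseline of the intervention (T0"), yet the plan gives it no stated use in estimating the effect. Two models fit the SAP sentence naturally:

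- **T0 as a repeated outcome.** The GEE runs over three visits, and the group-by-time term is a difference in change from T0.
- **T0 left out.** The GEE compares the groups on T1 and T2 only.

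Both are valid under randomisation, but neither is as precise in large samples as conditioning on T0. The two can also give different estimates from the same data, and with no contrast named the analyst could choose between them after seeing results. In a trial of 27 patients, avoidable variance matters.

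**Working it through.** **The plan's own figure.** The Protocol states: "A sample size of at least 26 has 80% power to detect the largest effect size of 0.5", and "An alpha level of 0.05 was used". It names neither the test nor the metric of 0.5. A total of 26 is reproduced by a two-sided point-biserial correlation of 0.5 (power 0.806), and by a between-groups repeated-measures ANOVA with f = 0.5, two measurements and correlation 0.5 (power 0.806). A two-sided, two-group t-test with d = 0.5 would need 128. The present point does not change the stated 26.

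**Inputs.** Group sizes 13 and 14 (Protocol, Procedures). The correlation r between T0 and follow-up is not given; I assume 0.3 to 0.8. The ICC of 0.8 quoted for CAT is a property of the questionnaire, not a T0-to-day-30 correlation.

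**Variance of the treatment contrast**, as a multiple of that for a follow-up-only comparison, with equal variances at T0 and follow-up and complete data:

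- T0 left out: 1
- Change from T0: 2(1 − r)
- T0-adjusted: 1 − r²

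So adjusted/change = (1 − r²) / [2(1 − r)] = (1 + r)/2, and adjusted/left out = 1 − r².

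| r | adjusted/change | reduction | adjusted/left out | reduction |
|---|---|---|---|---|
| 0.3 | 0.65 | 35% | 0.91 | 9% |
| 0.5 | 0.75 | 25% | 0.75 | 25% |
| 0.6 | 0.80 | 20% | 0.64 | 36% |
| 0.7 | 0.85 | 15% | 0.51 | 49% |
| 0.8 | 0.90 | 10% | 0.36 | 64% |

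**Unequal variances.** With SDs s0 at T0 and s1 at follow-up, change minus adjusted variance is proportional to (s0² + s1² − 2r·s0·s1) − s1²(1 − r²) = (s0 − r·s1)². Left-out minus adjusted is r²s1². Neither is negative, so the ordering does not depend on equal variances; the change-score percentages do.

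**Chance T0 difference.** SE = √(1/13 + 1/14) = 0.385 SD. P(|difference| ≥ 0.5 SD) = 2[1 − Φ(0.5/0.385)] = 0.194. The 95% range is ±1.96 × 0.385 = ±0.75 SD. Given a T0 difference D, and equal variances, the left-out contrast is shifted by r·D and the change contrast by −(1 − r)·D. At r = 0.5 and D = 0.5 SD, each shift is 0.25 SD in size, in opposite directions.

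**Small-sample cost.** Estimating one slope multiplies the adjusted variance by about 1 + 1/(N − 4). With N = 27 this is 1 + 1/23 = 1.04, so at r = 0.5 the ratio is 0.75 × 1.04 = 0.78. With only the 14 patients complete at T2 it is 1 + 1/10 = 1.10. The ratio is then 0.75 × 1.10 = 0.83 at r = 0.5, but 0.90 × 1.10 = 0.99 against change scores at r = 0.8, and 0.91 × 1.10 = 1.00 against the left-out model at r = 0.3. At those two ends the gain disappears.

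**Power**, 13 against 14, two-sided 0.05, complete data, r = 0.5, slope cost included:

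| Reading of 0.5 | T0 left out | change | adjusted |
|---|---|---|---|
| d = 0.5 | 0.24 | 0.24 | 0.29 |
| f = 0.5 (d = 1.0) | 0.70 | 0.70 | 0.80 |

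**The case against.** The strongest reply is that the SAP is silent, and silence is not a decision. A reader might infer that the trial does not adjust for T0. The documents do not support that: no sentence says T0 is adjusted for, and none says it is not. A GEE can carry T0 as a covariate. This stands, and it limits the point to what the plan fails to specify.

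A reader might also infer that chance T0 imbalance is left untouched. That is not so under the change-score reading, which subtracts the T0 difference and leaves only over-correction through regression to the mean. Nor is imbalance a second harm on top of lost precision: over repeated randomisations it is already contained in the variances above.

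A third tempting step is to turn the ratio of 0.75 at r = 0.5 into a sample-size equivalent, 27/0.75 = 36 patients. That needs 27 complete records. Procedures reports 17 patients at T1, 14 with complete data at T2, and overall attrition of 52%. (14 complete of 27 would be 13/27 = 48% lost; either way, about half.) The SAP fills the gaps by EM. The formula cannot be carried over to such data unchanged.

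Finally, a group-by-time GEE is a legitimate estimator, and a constrained-baseline model would recover similar precision. Both are true. They do not explain why the plan should leave the choice open.

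**Conclusion.** The point holds as one of specification and precision. The SAP assigns T0 no role in the GEE and names no contrast, and T0 adjustment is at least as precise in large samples as either natural reading. The variance reduction is about 35% to 10% against change scores and about 9% to 64% against a model without T0, for r from 0.3 to 0.8. This rests on an assumed r and complete data, and the change-score figures also on equal variances. With about half the day-30 data missing or imputed, the gain will be smaller, and it may vanish at the unfavourable ends of the range.

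A T0 difference of 0.5 SD or more would arise by chance in about 19% of trials of this size. The resulting error is conditional on the realised allocation; it is not bias under randomisation. The documents do not support reading this as an invalid analysis, or as a deliberate choice not to adjust. The change is worth making because it costs little and settles which estimate is the intervention effect.

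**What to change.** State in the SAP that, for each of CAT, CSSAQ and PEFR, the GEE takes T1 and T2 as responses, with group, visit, group-by-visit and the patient's own T0 value as covariate. An equivalent constrained-baseline model, with T0 kept as a response and its mean held common to both groups, would also serve. Name the T0-adjusted group differences at day 30 and day 7 as the reported effects.

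The cost is a sentence or two in the SAP and one degree of freedom per outcome; no new data are needed. Procedures already reports follow-up counts and attrition, so if the model is adopted after the data have been seen, it must be labelled a post hoc change. Adjustment does not cure the unequal dropout (30% experimental, 71% control), which needs its own treatment.

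### Three outcomes at two follow-ups share one p < .05 rule, with no primary outcome, deciding contrast or multiplicity adjustment; Holm would repair this only if the single EM fill-in is also replaced

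*SAP*

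**What the plan says.** The SAP (Statistical Analysis) gives one sentence on efficacy, "The intervention effect was evaluated using the generalized estimating equation (GEE) statistical method", and one decision rule, "Two-tailed tests were conducted, and p-values less than .05 were considered statistically significant". It also specifies intention-to-treat analysis with expectation-maximization (EM) for missing data.

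The protocol (Procedures) says that at baseline "the two groups took pre-tests, which measured the Chinese version of the CAT, the CSSAQ, and the PEFR, within 48 hours of hospitalization". Its follow-up visits are given as "the 7th day (T1) and the 30th day (T2) of the intervention to evaluate the effect of the intervention on pulmonary function". That makes three outcomes and two follow-ups.

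The sample-size statement (Protocol, Design and Participants) reads "A sample size of at least 26 has 80% power to detect the largest effect size of 0.5", followed by "An alpha level of 0.05 was used". It names no outcome, test or time point, and alpha is not divided. Neither document contains a primary outcome, a testing order, a deciding visit or an adjustment for multiple tests.

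**The concern.** The rule as written applies separately to every effect test that is reported. With three outcomes and two follow-ups, an ineffective intervention has several chances to produce p < .05. The plan has no rule for reading one significant result among several, so any one of them could be reported as the effect of the training. In a trial of 27 patients, that isolated finding could become the conclusion.

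**Working it through.** **The plan's own figure.** The test behind N = 26 is not named. A two-sided point-biserial correlation of 0.5 gives exactly 26. A repeated-measures ANOVA between-groups test (f = 0.5, two measurements, correlation 0.5) also gives 26. A two-group comparison with a standardised difference of 0.5 needs 63 per arm by the normal approximation. No reading that reproduces 26 points to one of the three outcomes, so the calculation does not identify a primary.

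**Inputs.** From the documents: per-test alpha .05 two-sided, three outcomes, two follow-ups, 13 v 14 allocated, 17 with day-7 data. Assumed, because the documents give none: correlation between outcomes 0 to 0.9, and between the T1 and T2 contrasts 0.5 to 0.9. A shared baseline with exchangeable errors gives 0.5.

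**Independent tests, as an upper reference.** 1 − 0.95⁶ = 0.265 for six contrasts; 1 − 0.95³ = 0.143 for three tests.

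**Correlated tests, each at nominal 5%.** Chance of at least one p < .05 among six when there is no effect, from 1,000,000 draws of correlated normal statistics:

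| Outcome correlation | T1–T2 correlation | Any of six |
|---|---|---|
| 0 | 0.5 | 0.248 |
| 0.3 | 0.5 | 0.238 |
| 0.5 | 0.5 | 0.220 |
| 0.7 | 0.7 | 0.177 |
| 0.8 | 0.8 | 0.149 |
| 0.9 | 0.9 | 0.116 |

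One test per outcome gives 0.143, 0.125 and 0.084 at outcome correlations 0, 0.5 and 0.9.

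**Does each test hold 5%?** The SAP does not state the GEE variance estimator. With 13 v 14 and complete data, an uncorrected robust Wald z has about 7% error per test. Holm over six on those p-values gives 0.048–0.097. A corrected (Mancl–DeRouen type) variance with a normal reference gives 0.032–0.063. An n − 1 variance with a t reference gives 0.049–0.050 per test and 0.024–0.047 after Holm.

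**Effect of the EM step.** These checks assume 10 v 7 observed at T1 (the total of 17 is stated, the split is not) and 9 v 4 at T2. The T2 numbers follow from the stated attrition: 13 × 0.70 = 9.1 and 14 × 0.29 = 4.1. Loss is taken as completely at random, and Welch t is applied to change.

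- Fill-in pooled across arms: Holm over six gives 0.029–0.036.
- Fill-in from arm-specific means with a common slope on baseline (T1–T2 correlation 0.5, outcome correlation 0 to 0.8): about 17% error per test at T1 and 29% at T2; any of six 63–79%; Holm over six about 36–49%.

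The second failure is not bias. Filled values are treated as if they had been observed, so the variance is too small. The SAP does not say whether the EM model includes arm, so both readings are open.

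**Power cost.** A test with 80% power at .05 has noncentrality 1.960 + 0.842 = 2.802. At .05/6 = .0083 the critical value is 2.638, and Φ(2.802 − 2.638) = Φ(0.164) = 0.565.

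**The case against.** The number of tests is not stated. The SAP's GEE sentence could mean a group effect, an omnibus group-by-time test or visit contrasts, so six is a reading of the design. The protocol's stated aim is pulmonary function, and PEFR is the only lung-function measure of the three. A PEFR-led analysis with one contrast is plausible and would stay at 5%. That stands as a possibility, but neither document makes the choice, and PEFR alone still leaves T1 against T2 open.

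A reader might infer that the trial's overall false-positive rate is 12–25%, or that the plan breaks a promise of 5% overall. The documents support neither. They claim no familywise control, do not say that one significant result counts as success, and give no correlations. The ranges describe what follows if the rule is applied to every contrast.

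A reader might also infer that Holm by itself brings the error back to 5%. It does not if single EM-filled values are analysed as observed data. In that case the fill-in could be a larger source of error than multiplicity. The EM reading is not certain either, since the protocol (Procedures) says "1M follow-up (T2) analyses were performed among the 14 participants with complete data", which could be taken as a complete-case analysis at that visit.

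Finally, reporting all estimates with intervals and labelling them exploratory would prevent most over-claiming without a formal adjustment. That is fair if no confirmatory claim is made. If one is made, an adjustment or a demonstrably pre-specified primary is needed.

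**Conclusion.** The point holds in a limited form. The plan applies one unadjusted p < .05 rule to three outcomes at two follow-ups and names nothing as deciding. If there is no effect and each test holds 5%, at least one significant result is expected about 12–25% of the time with six contrasts, or 8–14% with one test per outcome. Both ranges rest on the assumed correlations, and every setting examined exceeds 5%.

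Holm over six gives about 2–5% with complete data (13 v 14), a variance that holds its level and a t reference. With arm-specific single fill-in under the stated assumptions it still gives about 36–49%. Neither figure covers outcome-related loss, whose bias Holm does not remove. The size of the problem is therefore moderately certain; the omission itself is plain.

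**What to change.** Amend the SAP and reanalyse as follows.

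1. Define one family of six group-by-time contrasts: T0 to T1 and T0 to T2 for CAT, CSSAQ and PEFR.
2. Fit the GEE to the observed data, or use multiple imputation with its proper variance, instead of single EM-filled values.
3. Use a small-sample-corrected variance with a t reference.
4. Apply Holm across the six and claim an effect only on adjusted p-values.
5. Report all six estimates with 95% CIs, and label results that reach only unadjusted p < .05 exploratory.

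Naming a single primary now is not an equivalent remedy. The protocol already reports follow-up losses, so the choice should be labelled post hoc and stay inside the family unless dated evidence shows it was pre-specified.

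The report should not say that Holm restores 5% on EM-filled data or removes bias from losses. The 2–5% figure is for complete data and should not be carried over to 9 v 4 observed at T2.

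**Cost.** No new data are needed, but software other than the named package may be. Power per contrast falls from 80% to about 56% at the strictest Holm step. The protocol does not define its effect size of 0.5. With 13 v 14, power falls from 24% to 8% if it is a standardised mean difference, or from 82% to 56% if it is a correlation (standardised difference 1.155); both readings are assumptions.

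A separate inconsistency, not part of this point, should also be reconciled. Fourteen complete at T2 is 1 − 14/27 = 48% attrition, while the stated 52% implies 13 (1 − 13/27 = 0.519).
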